9.2.8. Visit Windowing

In analysis of data summarized by study visit, all data collection will be reassigned a study visit where data is scheduled for collection based on the actual days relative to Baseline. All visits will be assigned a target study day. Baseline will have a target study day of 1. For each assessment, the post-Baseline period will be divided up using the scheduled visit's target day.

The lower bound of each visit interval will be evaluated as the mid-point between the target day and the previous visit's target day in the following manner: study day interval lower bound = ceiling(target study day - ((target study day - last target study day)/2)). Table 3 shows an example of visit windowing that will be used to summarize by-visit vital sign data. Other data will be summarized similarly in accordance to their SoA (Protocol Table 1).

Table 3: Visit Windows Used to Summarize By-visit Vital Signs Data

| Scheduled Visit | Target Study Day | Study Day Interval |
|-----------------|------------------|--|
| Baseline | 1 | Last measurement on or prior to first dose of study drug |
| Day 2 | 2 | 2 to 3 |
| Day 5 | 5 | 4 to 6 |
| Day 8 | 8 | 7 to 9 |
| Day 11 | 11 | 10 to 12 |
| Day 14 | 14 | 13 to 14 |
| Day 15 | 15 | 15+ |

If more than 1 value is mapped to the same scheduled visit, the closer of those values will be considered for summarization. If multiple records exist with the same distance from the target study day, the last occurrence will be used. Visit windows are intended to be contiguous such that all data collected at all post-Baseline visits, whether scheduled or unscheduled, will map to one of the visits.

The visit displayed on data listings will be reflective of the scheduled visit label as reported on the CRF. Study days relative to Baseline will be displayed for each visit so it is apparent which visit the data may have been reassigned to in the summaries.

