**Table 2: Schedule of Pharmacokinetic/Pharmacodynamic and Safety Assessments on Day 1 and Day 15**

Time point (h) a	Pre-dose b	0	1	2	3	4	5	6	8	12	24
ALXN1840 (total Mo) and PUF Mo PK	X		X	X	X	X	X	X	X	X	X
Plasma total Cu, ceruloplasmin, ceruloplasmin-bound Cu, and LBC	X		X	X	X	X	X	X	X	X	X
ECG (triplicate)	X					X					

a Time points are relative to dosing (0 hours) on Day 1 and Day 15.

b Pre-dose should be collected within 1 hour prior to dosing.

Note 1: Windows for PK/PD time points will be defined as  $\pm 10\%$  of the nominal time point.

Note 2: The 24-hour PK/PD samples after Day 1 and Day 15 dosing are to be collected at pre-dose on Day 2 and at approximately 0800 am on Day 16.

Note 3: When multiple procedures are scheduled to occur at the same time, the following order of events should be strictly adhered to whenever possible: ECG, vital signs, blood sampling, study intervention administration, and meal.

Abbreviations: Cu = copper; LBC = labile-bound copper; Mo = molybdenum; PK = pharmacokinetic; PUF = plasma ultrafiltrate.

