concentration cannot distinguish whether the Mo is complexed with Cu and albumin (as in TPC), free active ALXN1840 drug, intermediate hydrolysis products, or molybdate which may be from ALXN1840 hydrolysis. To better characterize the amount of non-TPC bound ALXN1840 and its degradation products, plasma ultrafiltrate Mo (PUF Mo), which represents the free parent drug (ALXN1840), short-lived intermediate hydrolysis products, and molybdate, will be measured. Total Mo and PUF Mo concentrations also include physiologic molybdate concentrations from dietary micronutrient molybdate intake. While it is not feasible to separate and quantify ALXN1840 directly in the plasma, total Mo PK and PUF Mo PK provide surrogate measures to characterize ALXN1840 exposure. To better characterize the ADME of ALXN1840, the PK of both total Mo and PUF Mo will be characterized and described.

Single dose administration of the enterically-coated ALXN1840 under fasted conditions in healthy participants resulted in a peak total Mo concentration, as stable TPC, at approximately 4.54 hours with a half-life of approximately 51 hours. In Study WTX101-HV-106, a 60-mg dose demonstrated a total Mo time to maximum concentration ( $T_{max}$ ) of approximately 6 hours with up to 14% of the total Mo represented as PUF Mo, which also peaked at approximately 6 hours post dose. By 24 hours, PUF Mo had declined to approximately 3-5% of the total Mo. These findings are consistent with results from the Phase 2 Study WTX101-201 in patients with WD. Given the much longer half-life of total Mo, a repeat dose study of 15 days duration will support steady state assessment of ALXN1840 ADME (as measured by total Mo and PUF Mo). In addition, complete collection of Mo over the ALXN1840 treatment period as well as the 15-day terminal elimination period may support a complete assessment of Mo balance for the study.

As this study represents the first repeat dose study in healthy participants, dosing duration will be limited to 15 days. Safety laboratory tests will be monitored at least every 3 days with individual and cohort stopping criteria in place if significant safety risks are identified. In addition, if findings of Cu depletion or toxicity are identified in the initial study group by Day 18, the dose of ALXN1840 may be reduced to 15 mg/day for the remainder of the enrolled participants.

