7.4.3.4. Electrocardiogram

All ECG data will be fully listed and changes from Baseline in ECG data (heart rate, PR interval, RR interval, QRS duration, QT interval) will also be summarized descriptively by scheduled visit.

All QT intervals will be corrected for heart rate according to Fridericia ($QTcF = QT/(RR^{1/3})$). At each time point, the number and percentage of participants falling into the following categories according to the International Conference on Harmonization (ICH) E14 Guidelines will be presented:

- QTc actual values: ≤ 450 ms, >450 to ≤ 480 ms, >480 to ≤ 500 ms, and >500 ms
- QTc increases from Baseline of >30 msec and >60 msec

Changes from Baseline in QTc will also be summarized. Further, ECG data will be classified by the Investigator as “normal,” “abnormal, not clinically significant,” “abnormal, clinically significant” or “indeterminate” at each timepoint assessed. Summary results will include the count and percentage of participants within each category at each visit.

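### The SAP visit windows leave the Day 1 4 h ECG, and the pre-dose one of the two Day 15 ECGs, out of the by-visit change tables for heart rate, PR, RR, QRS and QT

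*SAP*

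**What the plan says.** **Schedule.** Protocol Table 2 places triplicate ECGs at two times, pre-dose and 4 h, on each of Day 1 and Day 15.

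**Protocol analysis rule.** Protocol 9.4.2 averages the triplicate at each time point where ECGs are taken and assesses changes from the pretreatment baseline. SAP 4.1 declares no departures from the protocol.

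**SAP ECG summaries (7.4.3.4).** Four outputs are described, with different units:
- Changes from Baseline in heart rate, PR, RR, QRS and QT "will also be summarized descriptively by scheduled visit".
- QTc categories, including increases from Baseline above 30 and above 60 msec, by time point.
- A summary of QTc change from Baseline, with no unit given.
- The investigator's classification, made at each time point but counted by visit.

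All ECG data are also listed.

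**SAP windowing (9.2.8).** This governs data summarised by study visit. Table 3 is a vital-signs example, and other data are to be treated in the same way according to their own schedule. The rules that matter here are:
- The aim is that no record goes unplaced: "Visit windows are intended to be contiguous such that all data collected at all post-Baseline visits", scheduled or not, are meant to land in a window.
- The first target is fixed as follows: "Baseline will have a target study day of 1".
- The Baseline window holds the "Last measurement on or prior to first dose of study drug".
- Each later window opens at the midpoint between its target day and the previous one, rounded up.
- Ties are settled thus: "If multiple records exist with the same distance from the target study day, the last occurrence will be used".

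**The concern.** The windows work in whole study days and keep one record per visit. The Day 1 and Day 15 ECGs are planned within-day pairs, one before and one after dosing. A rule of one record per visit cannot hold such pairs, and Day 1 has no post-dose visit at all.

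What is at stake is the numerical description of ECG change after dosing. The Day 1 4 h recording is the only post-dose ECG that Table 2 schedules on that day. It lies close to expected peak exposure: Protocol 4.2 reports that a single fasted dose "resulted in a peak total Mo concentration, as stable TPC, at approximately 4.54 hours", and gives about 6 h for the 60 mg study. The Day 15 pre-dose recording would help to separate a sustained steady-state change from a peak-related one. For heart rate, PR, RR, QRS and uncorrected QT, the by-visit table is the only numerical change summary that the SAP specifies. A time point lost there appears in no other specified change table for those parameters. Heart rate, PR, QRS and QT are named safety endpoints in Protocol Section 3.

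**Working it through.** **Inputs.** ECG times come from Protocol Table 2. The Baseline target (day 1), Baseline content, window formula, closest-value rule and tie rule come from SAP 9.2.8. Day numbering comes from SAP 9.2.3 and the protocol.

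**1. Reproduce SAP Table 3.** Lower bound = ceiling(t − (t − previous t)/2), with targets 1, 2, 5, 8, 11, 14, 15:
- t = 2: ceiling(2 − 0.5) = 2
- t = 5: ceiling(5 − 1.5) = 4
- t = 8: ceiling(8 − 1.5) = 7
- t = 11: ceiling(11 − 1.5) = 10
- t = 14: ceiling(14 − 1.5) = 13
- t = 15: ceiling(15 − 0.5) = 15

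These match the printed windows 2–3, 4–6, 7–9, 10–12, 13–14 and 15+.

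**2. Earliest possible post-Baseline window.** If the first post-Baseline ECG visit is on day t, its lower bound is ceiling(t − (t − 1)/2) = ceiling((t + 1)/2). This gives 2 for t = 2, 3 for t = 5 and 8 for t = 15. For every t from 2 to 43 it is at least 2.

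**3. Place the Day 1 4 h ECG.** Its study day is 1 in protocol numbering, or 0 by the literal formula in SAP 9.2.3, because the analysis date is not after the first dose date. Both are below 2, so no post-Baseline window takes it. It is a post-dose value, so Baseline does not take it either. Five ECG visit schedules were tried (for example Days 1 and 15 only; the Table 3 days; Days 1, 15, 31 and 43), each with both day numberings. The result was the same in all ten combinations.

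**4. Place the Day 15 ECGs.** Both have study day 15 and target 15, so both are at distance 0. The tie rule keeps the later one. The 4 h ECG stays and the pre-dose ECG is dropped.

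**5. Count for the Table 2 ECGs.**

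| Time point | By-visit tables as written | By nominal time point |
|---|---|---|
| Day 1 pre-dose | Baseline | Baseline |
| Day 1 4 h | no cell | kept |
| Day 15 pre-dose | dropped | kept |
| Day 15 4 h | kept | kept |

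One of three post-Baseline cells survives, so two are lost.

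**6. Baseline read by date instead of time.** SAP 9.2.4 does not say whether the cut-off is by date or by clock time. Read by date, the Day 1 4 h ECG would be the last value on the first dose date and would become Baseline. The Day 1 change would still be lost, and every later change would be measured from a post-dose value.

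**The case against.** The best defence is that 9.2.8 was never meant for planned within-day ECGs. Table 3 is only an example for vital signs, and other data follow their own schedule. Protocol Table 1 sends the Day 1 and Day 15 ECGs to Table 2, which is laid out by time point. Applied literally, the tie rule could even discard members of a triplicate, so it more plausibly concerns repeat or unscheduled records. Protocol 9.4.2 already supplies a time-point approach. It can also be argued that Day 1 is the Baseline visit, so the stated aim for post-Baseline visits is not strictly breached. This may well describe the intent, but the SAP states no exemption and 7.4.3.4 chooses the visit as the unit. By contrast, SAP 7.5.1 and 7.5.2 ask for PK and PD concentrations by day and time point. A programmer following the text would lose the cells.

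On importance, part of the objection stands. Safety analysis is descriptive, in about 17 participants, and the listings are complete. The retained Day 15 4 h ECG probably reflects higher exposure than the Day 1 one. With the protocol's half-life of about 51 h, daily dosing and an assumed one-compartment model, accumulation is 1/(1 − e^(−0.693 × 24/51)) ≈ 3.6-fold.

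A reader might go further and infer that the near-peak ECG vanishes from all change-from-Baseline output, or that QT safety monitoring is weakened. The documents support neither inference. The by-visit sentence does not name QTc, and the QTc categories, including the two thresholds for increase from Baseline, are by time point. The QTcF stopping rule in Protocol 6.6.1.4 acts on individual triplicate ECGs, and Protocol 7.1 requires review of the ECG printed at collection.

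**Conclusion.** The point holds for the by-visit continuous tables of heart rate, PR, RR, QRS and QT. As written, the Day 1 4 h ECG has no cell and the Day 15 pre-dose ECG is displaced, for every participant. This conflicts with Protocol 9.4.2 and with the SAP's own aim for its windows. The investigator-classification counts, being by visit, are exposed to the same rule. For the continuous QTc change the SAP gives no unit, so the effect there is undetermined.

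The count of two in three refers to Protocol Table 2 only. The ECG row of Protocol Table 1 could not be read in the text available, so this is not the share of all post-Baseline ECGs that is lost. The Day 1 result does not depend on that row. The conclusion assumes that distance from target is measured in whole study days, as 9.2.8 does, and that Baseline is cut at the time of first dose. No data are lost. The defect is in the summary tables, is modest in size and is easily corrected.

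**What to change.** In SAP 7.4.3.4 and 9.2.8, state that scheduled ECGs are exempt from day-level visit windowing and from the last-occurrence rule. Summarise changes from the pre-dose Baseline in all ECG parameters, QTcF included, by nominal day and time point: Day 1 4 h, Day 15 pre-dose, Day 15 4 h, and any other scheduled ECG day. Use the triplicate mean, as Protocol 9.4.2 requires. Count the investigator classification on the same basis, and say that the ECG Baseline is cut by clock time and not by date.

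The cost is a few sentences in the SAP and a few extra table rows. No new data are needed and the protocol does not change.

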9.3. Additional Details on Statistical Methods

Not applicable.
